To accomplish these goals, our outpatient clinic is open Monday thru Friday offering 4 different appointment times. All patients that are referred to our clinic for TAP, first receive a vein evaluation to see if the patient is a candidate for peripheral IV therapy. At our clinic, approximately 68% of our TAP's are performed peripherally. This eliminates the risk of a central line infection and any alteration in activities of daily living, such as bathing(Kramer, 2016), (Shang, Ma, Poghosyan, Dowding, & Stone, 2014),(Keller et al., 2018; McDiarmid, 2015).

Our hypothesis, is that the 20-gauge BD Nexiva Diffusics catheter provides the same efficacy as current practice with no increase in adverse events for patients undergoing therapeutic apheresis. The results from our study will be significant because if the 20 guage needle is equally effective for TAP, it can increase the number of patients that would be candidates for peripheral therapy. Therefore, decreasing the need for central venous access, which place the patient at an increased risk of infection. Our study is a comparison of 2 types of infusion catheters. The standard of care is an 18-gauge autogard catheter (control group) which will be compared to the 20-gauge BD Nexiva Diffusics (intervention).

- P patients who require therapeutic apheresis procedures (TAP)
- I use of 20G BD diffusics catheter during apheresis
- C use of 18 G standard of care IV catheter during apheresis
- O no difference in efficacy and no increase in safety events

Concise Summary of Project

This is a randomized pilot study of TAP using the current standard of care catheter (SOC) vs the BD Nexiva Diffusics Catheter. It is a single blinded, randomized study. Data will be used to refine and power a full randomized control trial. For this study, a sample of 33 encounters in each group (total of 66 encounters). Our specific aim is to test the hypothesis that the 20-gauge BD Nexiva Diffusics Catheter provides the same efficacy and lower pain level with no increase in adverse events for patients undergoing apheresis treatments.

Randomization Procedure

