After an eligible participant is consented to the study the patient will be randomized without replacement to the use of one of the two catheters. Using a random number generator, numbers between (1-66) were randomly divided into two groups: SOC Control group and BD Intervention group (Figure 1). A study identification number (SID) key will be saved on a UTSW approved secure device and only the research coordinator will have access to the SID key showing which SID coordinates with each group. This will ensure that unblinding can occur is necessary and there is a backup to randomization.

The research coordinator will have 66 randomized envelops without replacement. Half of the envelops will be assigned to 18G catheter SOC (control) and the other half be assigned to

20G BD Nexiva Diffusics catheter (intervention). The PI will be blinded, therefore the PI will pick an envelope when patients are consented and ready for treatment. Participants will be randomized after they have consented to the study. Participants' will then be randomized to one of the two groups again at each encounter (i.e., SOC visit). Inside the envelope it will tell the investigator if the patient is in the control or intervention group of the study.

To promote a more representative sample, each patient may participate a maximum of 10 times.

Study procedure:

[figure not shown]
Each enrolled patient will participate in the study will be randomized at each encounter. During each encounter the following information will be captured:

- 1. CBC
- 2. Patient discomfort

level with placement of catheter

- 3. Inlet rate
- 4. Return line pressures
- 5. Procedures alarms
- 6. Procedure total time
- 7. Post procedure sample

Treating nurse (RN) will start the TAPs procedure with one of the 2 catheters. During the intervention period, the RN will be at bedside during as it is SOC in the Apheresis unit however for the purpose of this study the RN will have the study data collection form (DCF, Appendix1). The RN will complete the pre-assessment including a pain assessment to establish pain level prior to procedure that is currently documented in the electronic medical record. The patient will be asked to self-report the pain level after the return line has been started on the visual analog scale (VAS) Scale from 0mm to 100mm "0 being the lowest/ no pain, 100mm being the highest

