level of pain". The VAS scale will be used for both the SOC and intervention group to compare the pain level when starting the return line. The RN will collect a CBC before the start of the procedure which will be used in the programing of the TAP procedure. The RN will start recording the "inlet rate, return line pressures, and alarms" every 15 minutes until the procedure is completed.

Before patient disconnects, and after the completion of procedure sing the same therapeutic apheresis procedure access site, a blood sample will be drawn by the RN 2 lavender top tubes (4ml) for plasma hemoglobin test. The plasma hemoglobin test will be sent to the UTSW lab for analysis of hemoloysis and results will be sent back directly to the PI. Blood sample results will be collected by the PI or the study team in an excel spreadsheet (CRF) that will be saved on a secure drive on the UTSW campus.

Hemolysis is defined as the destruction of red blood cells which leads to the release of hemoglobin from the red blood cells into the blood plasma. Each patient will be tested for hemolysis by running plasma hemoglobin test after the procedure has finished. This will be collected in a two lavender tops (4ml) The cost for this test is covered by sponsor and because the patient has an indwelling access to venous blood there will no charge for drawing the sample.. There is no clinical suspicion that the use of the 20-gauge BD Nexiva Diffusics Catheter will increase this risk. Hemolysis will be scored dichotomously as present or absent for each encounter.

Pain is defined as any increase discomfort experienced by the patient associated with the apheresis procedure. The current standard of care is to ask the patient "are you having pain" and then ask them to rate the pain from 0 to 10. For this study, one additional question will be asked after the patient's vein has been accessed (IV catheter in place). The patient will self-report their pain using a 100 mm VAS scale. "*The VAS has been used by healthcare providers to measure the characteristics of disease severity in each patient individually*"(Klimek et al., 2017) Currently, all peripheral apheresis patients have some pain/discomfort while having a treatment, however; it is usually tolerated with minimal complaints.

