be replaced with the SOC 18-gauge catheter. Obtaining blood samples may cause some discomfort, feeling lightheaded, fainting, bruising, clotting, and bleeding from the site of the needle stick and, in rare cases, infection. The risks are mitigated by drawing blood from a line that has already been established as part of SOC.

There is a low risk of breach in confidentiality. Subjects will be assigned individual study identification (SID) numbers and no personal identifiers will be included in the final summary.

Patients who are randomized to the 20-guage needle group and who fail the intervention will be given the 18-guage standard of care needle. At the patient's next visit, the patient will once again be randomized. If the patient is randomized into the 20-guage needle arm and fails the intervention a second time, the patient will be removed from the study.

Procedures to Maintain Confidentiality

Study participants will be given a study identification (SID) number. Only the approved study personnel and the principal investigator have access to the database linking the SID to the patient name. This database is kept on a protected drive on a password protected computer. Paper or hard copy participant records will be kept in a locked file cabinet in a locked office. If any identifying information is transmitted, it will be done so via secure e-mail and/or dedicated fax machines.

Statistical Analysis Plan

All data will be first collected on the DCF (Appendix I) and then entered into an electronic spreadsheet (e.g., MS Excel) which will be converted to SAS v 9.4 for analysis. All statistical analyses will be performed at UTSW in a location with secure data encryption capability. Initially, the data will be summarized first using standard measures of central tendency (mean, median, standard deviation, and interquartile range) for each variable. These will be examined to support the assumption of being approximately normally distributed. Baseline characteristics will be summarized using appropriate parametric and non-parametric measures.

The primary hypothesis is that the 20-gauge BD Nexiva Diffusics catheter provides the same efficacy of current practice with no increase in adverse events for patients undergoing therapeutic apheresis. This will be examined in 2 steps. First, ANOVA will be used to explore

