Instructions:	Please complete the following form except for the VAS scale. Must be completed by patient to measure the characteristics of pain severity. Please circle option that apply.					
Collect CBC	Yes	Νο				
Catheter type	18 GA BD Autogard	20 GA BD Nexiva Diffusics				
Vein diameter w/tourniquet:	Vein diameter w/o turniquet:	Vein diameter Procedure Running:				
Asses pain after return placement						
Please rate your current pain by drawing a vertical line across the bar below						

vere		Extremely Severe		
		Procedure d	ata	
tart time:				
Inlet rate	Return line pressures	Alarms	Comments	
	tart time:	tart time: Inlet rate Return line	Procedure da tart time: Inlet rate Return Alarms line	

Total Procedure time:	Procedure en	Procedure end time:		Final Inlet Volume/Blood Processed:	
Collect post proceduer Plasma Hemoglobin	Yes		No		

References

- Golestaneh, L., & Mokrzycki, M. H. (2013). Vascular access in therapeutic apheresis: update 2013. *Journal of clinical apheresis, 28*(1), 64-72.
- Kalantari, K. (2012). The choice of vascular access for therapeutic apheresis. *Journal of clinical apheresis*, 27(3), 153-159.
- Keller, S. C., Williams, D., Rock, C., Deol, S., Trexler, P., & Cosgrove, S. E. (2018). A new frontier: Central line–associated bloodstream infection surveillance in home infusion therapy. *American journal of infection control*, 46(12), 1419-1421.
- Kramer, N. (2016). Monitoring Central Line-Associated Bloodstream Infections (CLABSI) in Home Infusion. *Infusion*, 22(4), 35-44.
- McDiarmid, S. (2015). Reduce the risk of infection by reducing the need for central lines: using ultrasound guidance to establish peripheral access in patients with sickle cell disease undergoing red cell exchange apheresis. *Journal of clinical apheresis*, *30*(2), 98-99.

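### Pain is scored once, at return-catheter placement, so the plan cannot support a claim about pain over the whole procedure; one unrecorded component, catheter replacement, is described only for the 20G arm

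*Combined protocol and SAP*

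**What the plan says.** The specific aim (Concise Summary of Project) is to test whether the 20G catheter "provides the same efficacy and lower pain level with no increase in adverse events for patients undergoing apheresis treatments". The Study procedure section gives a broad definition: "Pain is defined as any increase discomfort experienced by the patient associated with the apheresis procedure". It adds that all peripheral patients have some discomfort during treatment.

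The measurement is narrower. The list of captured items gives patient discomfort "level with placement of catheter". The text says "one additional question will be asked after the patient's vein has been accessed (IV catheter in place", and elsewhere in the same section: "The patient will be asked to self-report the pain level after the return line has been started on the visual analog scale (VAS". The stated use of the score, in both groups, is "to compare the pain level when starting the return line". The form in Appendix 1 has one pain field, "Asses pain after return placement", and asks for current pain. The 15-minute recordings cover inlet rate, return pressures and alarms, but not pain.

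Potential Risks, in its part on the BD catheter, describes replacement by an 18G if alarms persist at the minimum inlet rate, and then states: "Patients who are randomized to the 20-guage needle group and who fail the intervention will be given the 18-guage standard of care needle". No matching provision is written for the 18G arm, and no repeat VAS is planned after a replacement. The Statistical Analysis Plan names no pain analysis.

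**The concern.** The aim and the definition concern the procedure, whereas the score concerns one moment near its start. Two sources of discomfort can arise after that moment: return flow, and placement of a second return catheter when the 20G fails. Neither is recorded as study data.

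The second source is uneven between the arms, because replacement is described only for encounters randomised to the 20G. On the form as written, such an encounter would hold the score from the smaller catheter and nothing for the 18G placed afterwards. A report of less pain during apheresis with the 20G could then include patients who had two return catheters placed, the second being the control device. The protocol intends the pilot data to refine and power a full trial, so a misread pain difference could carry forward.

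**Working it through.** **1. Claim against measure.**

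| Element | Scope | Where |
|---|---|---|
| Aim | Patients undergoing apheresis | Concise Summary of Project |
| Definition of pain | Discomfort linked to the procedure | Study procedure |
| Named contrast | Start of the return line | Study procedure |
| Score collected | Current pain after return placement, once | Appendix 1 |
| Repeated recordings | Inlet rate, return pressures, alarms | Study procedure |

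The score fits the named contrast but not the aim or the definition.

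**2. The plan's own figures.** There is none to reproduce for pain. The protocol gives 33 encounters per group without alpha, power, effect size or SD, and it gives no failure rate and no VAS value. All inputs in steps 3 to 5 are therefore assumptions.

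**3. Replacement component.** Let P be the placement score and R the pain of the replacement placement. In a failed 20G encounter, the worst of the two is max(P, R), so the present form misses max(P, R) − P, which is never negative. In other encounters this component is zero. If a share f of 20G encounters fails and the mean excess in those is e, the 20G mean worst pain is understated by f × e (mm):

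| f | e = 10 | e = 20 | e = 30 | e = 40 |
|---|---|---|---|---|
| 5% | 0.5 | 1.0 | 1.5 | 2.0 |
| 10% | 1.0 | 2.0 | 3.0 | 4.0 |
| 20% | 2.0 | 4.0 | 6.0 | 8.0 |
| 30% | 3.0 | 6.0 | 9.0 | 12.0 |

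If the replacement hurts no more than the first placement, e = 0 and nothing is missed on a worst-pain scale.

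The failure share that would cancel an observed 20G advantage D is f = D / e:
- D = 5 mm: 5/20 = 25%, 5/30 = 17%, 5/40 = 12.5%.
- D = 10 mm: 10/20 = 50%, 10/30 = 33%, 10/40 = 25%.

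**4. Adding return flow.** Let g be the unrecorded return-flow difference in mean pain, 20G minus 18G. Nothing in the documents fixes its sign. Treating the two components as additive, the total omitted difference is f × e + g. With f = 20% and e = 20 mm, f × e = 4 mm. For g from −10 to +10 mm, the total runs from 4 − 10 = −6 mm to 4 + 10 = +14 mm. The net direction is undetermined.

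**5. Scale.** With 33 per group, two-sided 0.05, 80% power and encounters treated as independent, the detectable difference is (1.960 + 0.842) × SD × √(2/33) = 0.69 × SD. That is 13.8 mm at an assumed SD of 20 mm and 17.2 mm at 25 mm. Every entry in step 3 is below 13.8 mm.

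**The case against.** A reader might infer that the single VAS biases the whole pain comparison towards the 20G. The documents do not support that, for four reasons.

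- **Return flow occurs in both arms and is missed in both.** The protocol says all peripheral patients have some discomfort during treatment. It does not say this is worse with the 20G. The 20G drawbacks listed in Potential Risks are longer time and an inadequate return rate, not pain. Background and Significance expects the larger needle to cause more discomfort.
- **For the contrast the protocol names, pain when the return line is started, one score at placement is largely aligned.** On that reading the defect is one of wording, and stating placement pain as the target would cure it. This stands, and the fix allows for it.
- **Part of the replacement argument is inference.** The text says the catheter is replaced; a new puncture is a reasonable reading but is not stated. Nor do the documents say how failed encounters enter the analysis.
- **The millimetre figures rest on assumptions.** A large e requires the 18G replacement to hurt much more than the first 20G placement, which comes close to presuming the advantage under test.

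It can also be said that a standard-of-care 0-10 rating exists and that the form has a comments column. The timing of that rating is not given, Sources of Research Material names the VAS as the self-reported pain data, and a comments column is not a pain measure. The pilot status lowers the stakes but does not remove the mismatch.

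**Conclusion.** The point holds as a mismatch between claim and measure. The one study pain score describes placement, while the aim and the definition describe the procedure, and later pain is recorded in neither arm.

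Only the replacement component has a known direction. If the result is read as whole-procedure pain, it can only flatter the 20G. This assumes that control catheters are not replaced, as the text implies by describing replacement for the 20G arm alone, and that no repeat score is taken. The stronger inference, that the pain comparison as a whole favours the 20G, is not supported: once return flow is included, the net sign is unknown.

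The size cannot be derived from the documents. The 0.5-12 mm range illustrates assumed failure shares of 5-30% and an assumed excess of 10-40 mm; the true figure could be zero. The change is worth making because it is cheap and works whichever arm bears the later pain.

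**What to change.** 1. Keep the present VAS and label it placement pain. Reconcile its two timings in Study procedure (catheter in place; return line started).
2. Add to the Data Collection Form, in both arms, one 100 mm VAS just before disconnection. It should ask for the worst return-site pain during the whole encounter, including any replacement catheter.
3. Add a pain analysis to the Statistical Analysis Plan. Compare both scores by randomised catheter, whatever catheter finished the encounter, and allow for repeated encounters per patient (up to 10), for example with a mixed model with a patient effect.
4. Base any claim of lower pain during apheresis on the end-of-procedure score. If that score is not added, limit the claim to placement pain in the aim and in the report.

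The cost is one more line on a form already at the bedside, a few seconds per encounter when the nurse is already drawing the post-procedure sample, and reliance on short recall. No clinical rule changes.

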Measures of Quality of Apheresis will include inlet rate, and return pressures, procedure time. These measures are all readily available in the electronic medical record (EMR) and are all currently recorded as standard of care. The inlet rate is defined as the percent of patient inlet rate divided by the maximum allowable inlet rate. Because inlet rates are different for each type of TAP has a different maximum inlet rate, this will allow standardization across procedures. The max inlet rate for Photopheresis is 50ml/sec, the max inlet for plasma exchange is 100ml/sec inlet for red blood cell exchange is 55ml/sec. In addition, the inlet rate for each participant in the intervention arm will be compared to the average of their last 5 procedures. This measure will compare the efficiency of the SOC verses the intervention.

Inclusion Criteria

- Adult (≥ 18 years old)
- Speaks and reads English
- A patient of the Apheresis clinic at UT Southwestern University Hospital and Clinics
- Scheduled to receive TAP (therapeutic plasma exchange, red blood cell exchange and extracorporeal Photopheresis) as standard of care

Exclusion Criteria

- Prisoners
- Persons under the age of 18 years
- Patient who are actively involved in chemotherapy

Sources of Research Material

There are three sources of data for this study: electronic medical record (EMR) and paper-and-pen data collection from the patient's bedside (Data Collection form), and lab results provided by the UTSW laboratory via EMR. The EMR data that will be collected will include demographic information such as: age, sex, race, ethnicity, and admission diagnosis. The paper-and pen-data collection will include the patient self-reported pain level (VAS Scale), CBC collection, procedure data (minutes, inlet rate, return line pressures and alarms) total procedure time and post procedure sample. The paper-and-pen data collection form (Appendix 1) will record data only during patients TAP's encounter. Blood sample will be obtained from a SOC line. An additional 8 ml's for blood will be drawn from the patients for research purposes. Results from the bloodwork will be provided by the UTSW laboratory via the patient's EMR.

Recruitment Methods and Consenting Process

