For this study, patients will be recruited from the Apheresis Unit at UT Southwestern University Hospital and Clinics by a member of the research team. A member of the research team will screen the electronic medical record to determine a patient's eligibility. If a patient appears eligible for the study a member of the research team will discuss eligibility criteria with a member of the clinical team (nurse manger, nurse, physician, resident, fellow, social worker). The researcher will communicate with the clinical team to ensure eligibility: adult (≥18 years old), speaks and reads English, admitted to the Apheresis Unit at UT Southwestern University Hospital and Clinics at the time of consent. All patients in this study will be able to provide selfconsent (read and speak English).

When a patient is deemed eligible, a member of the research team will discuss consent and study procedures with that patient, in a place that is comfortable for the patient. After being approached by a member of the research team, patients will have up to next visit to consider participation in the study. The study team expects recruitment of 30 participants to last approximately 8 months. (Table 1)

Potential Benefits

There may or may not be a direct benefit to the participants in this study. Any additional blood test result that seems out of the norm will be shared with the nurse on duty or treating physician. We would also hope to share this with the greater research and clinical community in hopes of finding an alternative way for apheresis patients to have therapeutic apheresis procedures with less pain and no increase in adverse events.

Potential Risks

Risks associated with BD Cather:

Longer procedure time might occur if the inlet rate of the treatment is slower. The patient will be informed of this during the ICF process. With smaller catheters there's a risk of not obtaining the appropriate return rate for the patient. When the return rate is out of the SOC parameters the SOC apheresis equipment (Optia or Cellex) will alarm. If the alarm sounds 3 times the RN will decrease inlet rate by 5 ml/sec until the minimum threshold is reached (if needed), which is 50 ml/sec for plasma exchange and 35 ml/sec for RBC exchange and 20 ml/sec for photopheresis. If the alarm continues to when the minimum threshold is reached the catheter will

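### Every inlet rate is stated per second, which is not physically credible, and the floor in the catheter-replacement rule carries that unit

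*Combined protocol and SAP*

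**What the plan says.** Study procedure, in the paragraph on quality measures, expresses the inlet rate as a percentage of a procedure-specific maximum so that the three procedure types can be put on one scale. The maxima are: "The max inlet rate for Photopheresis is 50ml/sec"; "the max inlet for plasma exchange is 100ml/sec"; and "inlet for red blood cell exchange is 55ml/sec". The same paragraph compares the inlet rate of intervention-arm participants with the average of their previous five procedures.

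Potential Risks uses inlet rates in the rule for a 20-gauge catheter that does not return well. After three alarms, "the RN will decrease inlet rate by 5 ml/sec until the minimum threshold is reached". The threshold is given as "which is 50 ml/sec for plasma exchange and 35 ml/sec for RBC exchange and 20 ml/sec for photopheresis". If the alarm persists at that floor, the catheter is exchanged for the standard 18-gauge one. The same section says that a patient who fails on the 20-gauge catheter is randomized again at the next visit, and leaves the study after a second failure in that arm.

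The Statistical Analysis Plan names plasma hemoglobin, minutes to complete the procedure and adverse events, and adds a secondary analysis of return pressure. It names no analysis of inlet rate.

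**The concern.** A rate in tens of millilitres per second is a rate in litres per minute. That is hard to reconcile with drawing blood from a peripheral vein, which suggests that the unit is mislabelled throughout.

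Two uses are affected. The more important is the replacement rule: a floor that cannot be a real flow rate cannot be applied as written, and staff would have to correct it silently. Reaching the floor with a continuing alarm appears to be what the protocol counts as failing the intervention, and two such failures remove a patient. The rule therefore bears on which 20-gauge encounters are completed on the assigned catheter and on who stays in the study.

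The second use is the denominator of the percent-of-maximum measure. Readings from the bedside form and from earlier procedures are set against the stated maxima, so the unit has to be right and common to both sides. The pilot is also meant to inform a full trial, and the unit could carry forward into it.

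**Working it through.** **Inputs from the documents.** Maxima: 50, 100 and 55 ml/sec (photopheresis, plasma exchange, red cell exchange; Study procedure). Floors: 50, 35 and 20 ml/sec (plasma exchange, red cell exchange, photopheresis; Potential Risks). Step: 5 ml/sec (Potential Risks). The documents derive no volume from these rates, and no sample-size figure depends on them, so there is no result of the plan's own to reproduce.

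**Conversion.** L/min = ml/sec × 60 / 1000. L per 15 minutes = ml/sec × 900 / 1000. Fifteen minutes is used as a convenient unit of time because readings are taken "every 15 minutes until the procedure is completed".

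| Figure | ml/sec | L/min | L per 15 min |
|---|---|---|---|
| Maximum, plasma exchange | 100 | 6.0 | 90 |
| Maximum, red cell exchange | 55 | 3.3 | 49.5 |
| Maximum, photopheresis | 50 | 3.0 | 45 |
| Floor, plasma exchange | 50 | 3.0 | 45 |
| Floor, red cell exchange | 35 | 2.1 | 31.5 |
| Floor, photopheresis | 20 | 1.2 | 18 |
| Step | 5 | 0.3 | 4.5 |

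The maxima span 45 to 90 L and the floors 18 to 45 L per 15 minutes. The step is a change in rate, not a flow, so it is kept apart from those ranges.

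**Plausibility.** Assumption, not in the documents: adult blood volume of 3 to 8 L, chosen wide.

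- Lowest floor (20 ml/sec): 18 / 8 = 2.25 to 18 / 3 = 6 blood volumes every 15 minutes. One blood volume would pass in 3000 / 20 = 150 to 8000 / 20 = 400 seconds.
- Highest maximum (100 ml/sec): 90 / 8 = 11.25 to 90 / 3 = 30 blood volumes every 15 minutes. One blood volume would pass in 3000 / 100 = 30 to 8000 / 100 = 80 seconds.

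Blood is returned during the procedure, so these are throughputs and not losses. They are still not credible through a peripheral line at any point in the assumed range.

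**Effect on the percentage.** If numerator and denominator share a unit, the label cancels. The floors as percentages of the maxima are 50 / 100 = 50%, 35 / 55 = 63.6% and 20 / 50 = 40%, whatever the unit. If a per-minute reading were divided by a per-second maximum, every percentage would fall 60-fold: 100 / (100 × 60) = 1.67% in place of 100%.

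**The case against.** The strongest reply is that nothing in the documents disagrees with anything else. Every inlet rate is in ml/sec and no other flow unit appears. A reader might infer an internal contradiction from the 15-minute readings, but a recording interval only says how often values are written down and places no limit on flow. This stands: the case rests on physical implausibility and on an assumed blood volume.

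A reader might also infer that a trial endpoint is wrong 60-fold. The documents do not support that. Inlet rate is a quality measure without a named analysis in the Statistical Analysis Plan, and the percentage is distorted only if one side of the ratio is in a different unit. Nothing in the protocol calls for a conversion, and it describes these values as already recorded in routine care.

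Nor do the documents show that any encounter would be handled differently. Replacement needs a continuing alarm as well as the floor, and staff may simply follow the device display. The link from the floor to removal is also partly inferred, because the protocol never expressly defines failing the intervention.

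Finally, the inlet-rate column of Appendix 1 appears without a unit, but that table is broken in the available text. The missing unit may come from the extraction and is not counted as a defect of the form.

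These points limit the consequences. None makes the stated unit credible, and a replacement threshold should not depend on staff reading it as something other than what is printed.

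**Conclusion.** The unit is wrong as written, and it is the unit of a decision threshold. As stated, the maxima are 3.0 to 6.0 L/min, the floors 1.2 to 3.0 L/min and the step 0.3 L/min. The conclusion needs one outside assumption, the adult blood volume, and holds across the whole 3 to 8 L range.

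The main consequence is for the rule that exchanges the 20-gauge for the 18-gauge catheter and, on the natural reading, for what counts as failure and later removal. The effect on the percent-of-maximum measure is conditional: none if the units match, 60-fold if a per-minute reading meets a per-second maximum. The documents do not establish bias in a planned analysis.

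**What to change.** 1. Verify the inlet-rate unit against the apheresis devices, and correct the maxima in Study procedure and the step and floors in Potential Risks together, so that the two sections stay aligned.
2. State that numerator and denominator of the percent-of-maximum measure use that one unit, including in the comparison with the last five procedures.
3. Make sure the inlet-rate column of Appendix 1 carries the unit.

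The clinical team must confirm the values. No rate, unit or clinical rule is proposed here. The cost is protocol and form wording only, with no new data and no change to sample size or design.
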